#### **9.1.2 Definition of Missing Data Imputation**

##### **Non-Responder Imputation (NRI) Approach**

The NRI approach will categorize any subject who has missing value for categorical variables at a specific visit as non-responder for that visit. In addition, subjects who prematurely discontinue from study drug will be considered as non-responders for all subsequent visits after discontinuation.

**Observed Cases (OC)**

The OC analysis will not impute values for missing evaluations. In addition, the OC will not use values after premature discontinuation of study drug. This sensitivity analysis will only be applied to the analysis in Period 1.

**As Observed (AO)**

The AO analysis will not impute values for missing evaluations. Regardless of treatment switching or premature discontinuation of study drug, all observed data will be used in the analysis. The AO analysis will be applied to long-term efficacy analysis.

**Mixed Effect Model Repeat Measurement (MMRM) for Short-Term Analysis**

The repeated measure analysis will be conducted using mixed model including observed measurements at all visits. The mixed model includes the categorical fixed effects of treatment, visit and treatment-by-visit interaction, main stratification factors at randomization, and the continuous fixed covariates of baseline measurement. An unstructured variance covariance matrix will be used. The parameter estimations are based on the assumption of data being missing at random and using the method of restrictive maximum likelihood (REML). The missing at random assumption is considered reasonable given the high placebo response rate typically seen in RA trials. Additionally in RA trials, the proportion of discontinuation is relatively small (10 – 15% only) and the rate of discontinuation due to lack of efficacy is generally low (< 5%).

**MMRM and Generalized Linear Mixed Model (GLMM) for Long-Term Analysis**

The repeated measure analysis will be conducted using mixed model including As Observed measurements at all visits. MMRM will be used for continuous endpoints and GLMM will be used for binary endpoints. The mixed models will include the categorical fixed effects of treatment, visit and treatment-by-visit interaction, and main stratification factor prior bDMARD use. For the MMRM analysis of change from baseline in continuous endpoints, the baseline measurement will be included as a continuous fixed

covariate. The categorical fixed effect of subject's discontinuation status may also be included in the model as appropriate. Unstructured, Toeplitz, compound symmetry, or other covariance structures may be considered.

### **Multiple Imputation (MI)**

The MI analysis will impute missing data multiple times under appropriate random variation and thus generate multiple imputed "pseudo-complete" datasets. Results will be aggregated across the multiple imputed datasets, overcoming drawbacks of the single imputation methods. LOCF will be first applied to augment data into monotonic missing pattern. PROC MI will be used to generate 5 datasets using the regression method. Specifically, visits will be imputed in order, where later visits are imputed by regressing upon all previous visits, baseline, treatment group, demographics and other key baseline characteristics. Analysis will first be performed on each of the multiple imputed datasets, and PROC MIANALYZE will then be used to aggregate the results for the final statistical inference. The imputation is based on assumption of data being missing at random. The missing at random assumption is considered reasonable given the high placebo response rate typically seen in RA trials. Additionally in RA trials, the proportion of discontinuation is relatively small (████████ only) and the rate of discontinuation due to lack of efficacy is generally low ██████████

## **9.2 Efficacy Analysis for Period 1**

### **9.2.1 Primary Efficacy Analysis**

The primary endpoint for US/FDA regulatory purposes is ACR20 response at Week 12. The primary endpoint for EU/EMA regulatory purposes is LDA (based on DAS28 (CRP)  $\leq 3.2$ ) at Week 12. Analyses will be conducted separately for US/FDA regulatory purposes and EU/EMA regulatory purposes; for each set of analysis, only one primary endpoint is specified.

Analysis of the primary endpoint will be conducted on the FAS based on randomized treatment groups (upadacitinib 15 mg QD, upadacitinib 30 mg QD and the combined

placebo groups). Point estimate and 95% CI using normal approximation will be provided for the response rate for each randomized treatment group. Comparisons of the primary endpoint will be made between each upadacitinib dose and the combined placebo group using the Cochran-Mantel-Haenszel test adjusting for stratification factor prior bMDARD use. Point estimate, 95% CI using normal approximation and p-value for the treatment comparison will be presented. Both nominal p-value constructed using the Cochran-Mantel-Haenszel test and adjusted p-value through the graphical multiplicity procedure described in Section 9.2.5 will be provided. For the primary analysis, non-responder imputation (NRI) will be used.

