5.3.3 Efficacy Variables

5.3.3.1 Period 1 Variables

5.3.3.1.1 Primary Variables

The primary endpoint in Period 1 is the proportion of subjects achieving ACR20 response (US/FDA regulatory purposes) or the proportion of subjects achieving LDA (EU/EMA regulatory purposes) at Week 12. Analyses will be conducted separately for US/FDA regulatory purposes and EU/EMA regulatory purposes; for each set of analyses, only one primary endpoint is specified.

ACR20 response rate will be determined based on 20% or greater improvement in TJC and SJC and ≥ 3 of the 5 measures of Patient's Assessment of Pain (VAS), Patient's Global Assessment of Disease Activity (VAS), Physician's Global Assessment of Disease Activity (VAS), HAQ-DI, or hsCRP.

LDA is defined as DAS28 (CRP) ≤ 3.2 . DAS28 (CRP) score will be determined based on a continuous scale of combined measures of TJC, SJC, Patient's Global Assessment of Disease Activity (PtGA) (in mm), and hsCRP (in mg/L) at Week 12.

$$\text{DAS28 (CRP)} = 0.56 \times \sqrt{(\text{TJC28}^*)} + 0.28 \times \sqrt{(\text{SJC28}^{**})} + 0.36 \times \ln(\text{hsCRP}^{\&} + 1) + 0.014 \times \text{PtGA}^{>>} + 0.96$$

* TJC28 refers to the Subject's total Tender Joint Count out of the provided 28 evaluated joints.

** SJC28 refers to the Subject's total Swollen Joint Count out of the provided 28 evaluated joints.

& hsCRP refers to the high-sensitivity c-reactive protein lab value. hsCRP unit in the DAS28 (CRP) equation is expressed as mg/L.

>> PtGA refers to the Patient's Global Assessment of Disease Activity.

where $\sqrt{}$ is square root and \ln is natural log.

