8.1.4.1.1 Primary Efficacy Variables

The primary endpoint in Period 1 (at Week 12) for US/FDA regulatory purposes is listed in Section 5.3.3.1.1. The primary endpoint in Period 1 (at Week 12) for EU/EMA regulatory purposes is also listed in Section 5.3.3.1.1. Analyses will be conducted separately for US/FDA regulatory purposes and EU/EMA regulatory purposes; for each set of analyses, only one primary endpoint is specified.

Analysis of the primary endpoint will be conducted on the FAS based on treatment as randomized. Comparison of the primary endpoint will be made between each upadacitinib group and the combined placebo groups using the Cochran-Mantel-Haenszel test adjusting for main stratification factors. For the primary analysis, Non-Responder Imputation (NRI) will be used. The analysis will be repeated using Observed Cases (OC). Supportive analysis will also be conducted on the Per Protocol Analysis Set.

The primary efficacy analyses will also be performed in demographic subgroups including age, gender, weight, body mass index, race, and geographical region to assess the consistency of the treatment effect. Additional subgroup analyses based on baseline disease characteristics and stratification factors will also be conducted.

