8.3 Randomization Methods

Subjects will be randomly assigned in a 2:2:1:1 ratio to one of the four treatment groups:

- Group 1: Upadacitinib 30 mg QD (N = 200) (Period 1) → Upadacitinib 30 mg QD (Period 2)
- Group 2: Upadacitinib 15 mg QD (N = 200) (Period 1) → Upadacitinib 15 mg QD (Period 2)
- Group 3: Placebo (N = 100) (Period 1) → Upadacitinib 30 mg QD (Period 2)
- Group 4: Placebo (N = 100) (Period 1) → Upadacitinib 15 mg QD (Period 2)

Randomization will be stratified by prior exposure to bDMARD (yes/no) and geographic region.

See Section 5.5.3 for details.

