## **4.3 Sample Size**

The planned total sample size of 600 for this study provides at least 90% power for a 21% difference in ACR20 response rate at Week 12 (assuming a placebo ACR20 response rate

of 37%), as well as at least 90% power for a 22% difference in LDA response rate at Week 12 (based on DAS28 [CRP] [assuming a placebo LDA response rate of 15%]), at two sided significance level of 0.025 and accounting for a 10% dropout rate. This sample size will also provide at least 90% power for most of the key secondary endpoints, including change from baseline in DAS28 (CRP), change from baseline in HAQ-DI, ACR50 response rate, CR based on DAS28 (CRP), and SF-36 PCS, at two-sided significance level of 0.025 and accounting for a 10% dropout rate.

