### **Other Baseline RA Disease Characteristics**

- Anti-cyclic citrullinated peptide (Anti-CCP) (units)
- Anti-CCP status: Positive or Negative
- Rheumatoid Factor (RF) (units)
- Rheumatoid Factor (RF) status: Positive or Negative
- Percentage of subjects on oral steroid at baseline
- Oral steroid dose (prednisone equivalent) at baseline

- DAS28 [hsCRP]
- DAS28 [ESR]
- DAS28 Categories:
  - DAS28 > 5.1 (High Disease Activity)
  - DAS28 ≤ 5.1
- Clinical Disease Activity Index (CDAI)
- CDAI categories:
  - CDAI > 22 (High Disease Activity)
  - CDAI ≤ 22
- Simplified Disease Activity Index (SDAI)
- SDAI categories:
  - SDAI > 26 (High Disease Activity)
  - SDAI ≤ 26

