### **9.2.3 Key Secondary Efficacy Analyses**

Ranked key secondary endpoints (at Week 12) for US/FDA regulatory purposes are:

1. Change from baseline in DAS28 (CRP);
2. Change from baseline in HAQ-DI;
3. Change from baseline in Short Form-36 (SF-36) Physical Component Score (PCS);
4. Proportion of subjects achieving LDA based on  $\text{DAS28 (CRP)} \leq 3.2$ ;
5. Proportion of subjects achieving Clinical remission (CR) based on DAS28 (CRP);
6. Proportion of subjects achieving LDA based on  $\text{CDAI} \leq 10$ ;
7. Change from baseline in morning stiffness (duration);
8. Change from baseline in Functional Assessment of Chronic Illness Therapy-Fatigue (FACIT-F).

Ranked key secondary endpoints (at Week 12) for EU/EMA regulatory purposes are:

1. Change from baseline in DAS28 (CRP);
2. Change from baseline in HAQ-DI;
3. ACR20 response rate;
4. Change from baseline in Short Form-36 (SF-36) Physical Component Score (PCS);
5. Proportion of subjects achieving Clinical remission (CR) based on DAS28 (CRP);
6. Proportion of subjects achieving LDA based on CDAI  $\leq$  10;
7. Change from baseline in morning stiffness (duration);
8. Change from baseline in Functional Assessment of Chronic Illness Therapy Fatigue (FACIT-F).

Other key secondary endpoints (at Week 12) for both US/FDA and EU/EMA regulatory purposes are:

1. ACR50 response rate;
2. ACR70 response rate;
3. Proportion of subjects achieving ACR20 response rate of Week 1.

For binary endpoints, frequencies and percentages will be reported for each randomized treatment group. Similar analyses as for the primary endpoint will be conducted.

For the major RA continuous endpoints DAS28 and HAQ-DI change from baseline, statistical inference will be conducted using analysis of covariance (ANCOVA) coupled with MI for missing data handling. Specifically, the ANCOVA model will include treatment as the fixed factor, and the corresponding baseline value and the stratification factor prior bDMARD use (Yes/No) as the covariates. For other continuous endpoints, statistical inference will be conducted using the MMRM model as described in

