**Table 4. Summary of Efficacy Variables and Corresponding Analyses for Efficacy Analysis in Period 1**

Efficacy Variables	Analysis Method
Primary Variables	

 
ACR20 response at Week 12a
 
LDA as measured by DAS28 (CRP) at Week 12b
 
	
 
Point estimate and 95% CI of the response rate for each upadacitinib dose group and the combined placebo group. The 95% CI will be based on normal approximation.
 
Point estimate, 95% CI and p-value for the treatment comparison between each upadacitinib dose group and the combined placebo group, where the p-value is constructed using the Cochran-Mantel-Haenszel test adjusting for stratification factor prior bDMARD use. Both nominal p-value and adjusted p-value through the graphical multiplicity procedure described in Section 9.2.5 will be provided. The 95% CI will be based on normal approximation.
 
Subgroup analysis.
 
Imputation: NRI for primary analysis and OC for sensitivity analysis
 
Analysis Set: FAS and Per Protocol Analysis Set as supportive analysis (NRI only).
 

Key Secondary Variables	

Binary Endpoints:
 
 
ACR50/70 response at Week 12
 
ACR20 response at Week 12b
 
ACR20 response at Week 1
 
Proportion of subjects achieving LDA based on DAS28 (CRP) <math>\leq 3.2^a</math>
 
Proportion of subjects achieving Clinical remission (CR) based on DAS28 (CRP)
 
Proportion of subjects achieving LDA based on CDAI <math>\leq 10</math>
 
	
 
Point estimate and 95% CI of the response rate for each treatment group. The 95% CI will be based on normal approximation.
 
Point estimate, 95% CI and p-value for the treatment comparison between each upadacitinib dose group and the combined placebo group using the Cochran-Mantel-Haenszel test adjusting for stratification factor prior bDMARD use. For ranked key secondary endpoints, both nominal p-value and adjusted p-value through the graphical multiplicity procedure described in Section 9.2.5 will be provided. The 95% CI will be based on normal approximation.
 
Imputation: NRI for primary analysis and OC for sensitivity analysis
 
Analysis Set: FAS
 

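### The EU primary endpoint, LDA by DAS28(CRP), is tested without adjusting for baseline DAS28(CRP): a valid test that gives up a modest amount of precision

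*SAP*

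**What the plan says.** **Endpoint.** Protocol 5.3.3.1.1 and SAP 9.2.1 define LDA by the Week 12 score alone: DAS28(CRP) at or below 3.2. SAP Table 4 lists it among the primary variables as "LDA as measured by DAS28 (CRP) at Week 12".

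**Test.** SAP 9.2.1 compares each dose with the combined placebo group "using the Cochran-Mantel-Haenszel test adjusting for stratification factor prior bMDARD use" (the abbreviation is misspelt in the SAP), with non-responder imputation and a normal-approximation interval. SAP 9.2.3 applies similar analyses to DAS28 remission and CDAI LDA. Protocol 8.1.4.1.1 asks for the "Cochran-Mantel-Haenszel test adjusting for main stratification factors". Protocol 8.3 names those factors: "Randomization will be stratified by prior exposure to bDMARD (yes/no) and geographic region". Baseline disease activity is not among them.

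**Baseline DAS28 elsewhere.** SAP 6.1 categorises it ("DAS28 > 5.1 (High Disease Activity"). In SAP 9.2.3 the ANCOVA for change in DAS28(CRP) takes "the corresponding baseline value and the stratification factor prior bDMARD use (Yes/No) as the covariates". SAP Table 3 uses baseline DAS28 as a subgroup factor, with an estimate and interval in each subgroup but no pooled, adjusted estimate. The further analyses of the primary endpoint in SAP 9.2.2 are Observed Cases and the Per Protocol set; neither adds baseline.

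**Status.** SAP 11.1 states that the primary analysis and Period 1 reporting were completed under version 2.0.

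**The concern.** LDA asks where a subject ends, not how far the subject has moved. Someone who starts at 4.5 must fall by 4.5 − 3.2 = 1.3; someone who starts at 7 must fall by 7 − 3.2 = 3.8. If Week 12 DAS28 is positively correlated with its baseline, baseline predicts LDA. An analysis that ignores it leaves explainable variation in the treatment difference, and the interval is wider than the collected data allow.

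The SAP uses baseline for the continuous form of the same score. Dichotomising the Week 12 value does not remove its dependence on baseline. What is at stake is the width of the interval around the LDA difference for each dose, and how far that estimate reflects chance differences in starting disease activity.

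**Working it through.** **Inputs from the documents.** SAP 4.3 plans LDA "assuming a placebo LDA response rate of 15"% and a 22-point difference, so 15% versus 37%; N = 600; two-sided 0.025 per dose; 10% dropout. The 2:2:1:1 allocation with pooled placebo gives 200 versus 200.

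**Inputs assumed.** The correlation ρ between baseline and Week 12 DAS28 is 0.3 to 0.6, with normal scores. For the 5.1 split only, baseline DAS28(CRP) has mean 5.7 and SD 0.95, so a fraction Φ((5.1 − 5.7)/0.95) = 0.264 lies at or below 5.1. None of these is in the documents.

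**1. The plan's own power.** With 180 per arm after dropout and mean rate 0.26:

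Φ[(0.22 − 2.2414·√(2·0.26·0.74/180)) / √((0.1275 + 0.2331)/180)] = Φ[(0.22 − 0.1036)/0.0448] = Φ(2.60) = 99.5%.

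With 200 per arm it is 99.8%. Keeping 200 and diluting both rates by 10% as non-responders (13.5% versus 33.3%) gives 99.4%. For 90% power, 97 per arm would do, or 97/0.9 ≈ 108 with dropout. The SAP's claim of at least 90% is correct, with a wide margin.

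**2. Unadjusted SE of the difference.** √(0.1275/200 + 0.2331/200) = 0.0425. The 95% half-width is 1.96 × 0.0425 = 8.3 points.

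**3. Adjusted for continuous baseline.** Let x be standardised baseline and p_k the response rate in arm k (0 = placebo, 1 = dose). The response probability is m_k(x) = Φ[(Φ⁻¹(p_k) − ρx)/√(1 − ρ²)], and

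V = E[m₀(1 − m₀) + m₁(1 − m₁)]/200 + Var(m₁ − m₀)/400.

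**4. Adjusted for the 5.1 split.** The same formula applies with two strata. At ρ = 0.4 the model gives LDA rates of 0.282 and 0.569 (placebo, dose) in the low stratum and 0.103 and 0.299 in the high stratum. So V = [0.264·(0.2023 + 0.2453) + 0.736·(0.0923 + 0.2095)]/200 + 0.0016/400 = 0.001705, and the SE is 0.0413.

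| ρ | SE, continuous | reduction | SE, 5.1 split | reduction |
|---|---|---|---|---|
| 0.3 | 0.0414 | 2.4% | 0.0418 | 1.5% |
| 0.4 | 0.0406 | 4.4% | 0.0413 | 2.7% |
| 0.5 | 0.0395 | 7.0% | 0.0405 | 4.6% |
| 0.6 | 0.0380 | 10.6% | 0.0394 | 7.1% |

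Reductions use unrounded SEs. Continuous adjustment takes the half-width from 8.3 to between 8.1 and 7.4 points (1.96 × 0.0414 and 1.96 × 0.0380), and lowers the variance by 5% to 20%.

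**5. Chance imbalance.** A one-SE baseline imbalance at 200 per arm is √(2/200) = 0.10 SD. Moving each arm by half of it shifts the difference by Φ(Φ⁻¹(0.37) + 0.05ρ) − Φ(Φ⁻¹(0.15) − 0.05ρ) − 0.22. This is 0.9, 1.2, 1.5 and 1.8 points at ρ = 0.3, 0.4, 0.5 and 0.6. At ρ = 0.4 that is 0.012/0.0425, about 0.3 of one SE.

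**6. Validity and power.** In simulation (10,000 trials each at ρ = 0.2, 0.4 and 0.6) the planned CMH test had type I error of 2.3% to 2.7% against a nominal 2.5%. At the planned effect and 180 per arm, adjustment moves power from 99.6% to between 99.7% and 99.9% (unpooled approximation). At a smaller effect, 15% versus 27% with 200 per arm, simulated power rose from 78.2% to 81.2% at ρ = 0.4 and from 76.9% to 86.5% at ρ = 0.6 (logistic model with baseline against CMH; 3,000 trials each).

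**The case against.** The strongest reply is that nothing here is an error. CMH on a randomisation factor is a valid test, the protocol specified CMH on stratification factors, and baseline DAS28 was never one of them. ANCOVA for a change score and CMH for a binary endpoint are different methods for different data, so using baseline in one and not the other is no contradiction. Power is so high that no decision at the planned effect could turn on this. Table 3 already plans estimates on either side of 5.1, and the first ranked EU secondary endpoint is baseline-adjusted. Period 1 is already reported.

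Most of that stands, and it rules out several stronger readings that a reader might infer:

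- **Bias or false positives.** Randomisation keeps the unadjusted difference unbiased, and the simulated type I error is at its nominal level.
- **Imbalance as a second defect.** Chance imbalance is already inside the unadjusted SE. It is the same loss of precision seen from another side, and adding the two counts it twice.
- **A known loss.** The direction follows from any positive correlation. The amount rests on a correlation the documents do not give.
- **An underpowered comparison.** The design figures give over 99%.
- **A departure from the protocol.** None arises over baseline DAS28. Leaving region out of the CMH strata is a separate matter.

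The reply does not dispose of one thing: separate subgroup estimates are not a pooled adjusted difference, and no planned analysis supplies one for LDA.

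**Conclusion.** The point holds as a modest, inexpensive gain in precision. At 15% versus 37% with 200 per arm, adjusting for continuous baseline DAS28(CRP) would cut the SE of the LDA difference by about 2% to 11% for an assumed correlation of 0.3 to 0.6. The dichotomy at 5.1 would recover about 1% to 7%, under the further assumption of mean 5.7 and SD 0.95. The gain lies in interval width, and would affect power noticeably only if the true effect were well below the planned 22 points. The planned test remains valid and the conclusion at the design effect is not in question. The calculation covers DAS28 LDA only. The same reasoning applies to DAS28 remission and CDAI LDA, but no size has been worked out for them.

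**What to change.** Leave the reported primary result as it is. Add one supportive analysis, labelled post hoc, beside it:

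- Fit a logistic model for Week 12 LDA on the FAS with the same non-responder imputation. Terms: treatment (15 mg, 30 mg, combined placebo), prior bDMARD use and continuous baseline DAS28(CRP).
- Standardise over all FAS subjects and report the marginal risk difference for each dose with a 95% CI. This keeps the risk-difference scale of the reported result; an adjusted odds ratio would be a conditional quantity.
- Use continuous baseline, not the 5.1 split, which gives up part of the gain.
- State how a missing baseline score is handled, so that the analysis stays on the full FAS; SAP 9.4.6 sets DAS28 to missing when any component is missing.
- Do the same for DAS28 remission, and for CDAI LDA with baseline CDAI as the covariate.

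The cost is a short SAP or report addendum and one further run on existing data. It needs no new data and no change to the testing procedure.

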### **9.2.2 Sensitivity Analysis of Primary Efficacy Variables**

The primary analysis for point estimate and CI will be repeated using Observed Cases without any imputation as a sensitivity analysis. This will be conducted on the FAS based on randomized treatment groups.

Supportive NRI analysis will also be conducted on the Per Protocol Analysis Set.

### **9.2.3 Key Secondary Efficacy Analyses**

Ranked key secondary endpoints (at Week 12) for US/FDA regulatory purposes are:

1. Change from baseline in DAS28 (CRP);
2. Change from baseline in HAQ-DI;
3. Change from baseline in Short Form-36 (SF-36) Physical Component Score (PCS);
4. Proportion of subjects achieving LDA based on  $\text{DAS28 (CRP)} \leq 3.2$ ;
5. Proportion of subjects achieving Clinical remission (CR) based on DAS28 (CRP);
6. Proportion of subjects achieving LDA based on  $\text{CDAI} \leq 10$ ;
7. Change from baseline in morning stiffness (duration);
8. Change from baseline in Functional Assessment of Chronic Illness Therapy-Fatigue (FACIT-F).

Ranked key secondary endpoints (at Week 12) for EU/EMA regulatory purposes are:

1. Change from baseline in DAS28 (CRP);
2. Change from baseline in HAQ-DI;
3. ACR20 response rate;
4. Change from baseline in Short Form-36 (SF-36) Physical Component Score (PCS);
5. Proportion of subjects achieving Clinical remission (CR) based on DAS28 (CRP);
6. Proportion of subjects achieving LDA based on CDAI  $\leq$  10;
7. Change from baseline in morning stiffness (duration);
8. Change from baseline in Functional Assessment of Chronic Illness Therapy Fatigue (FACIT-F).

Other key secondary endpoints (at Week 12) for both US/FDA and EU/EMA regulatory purposes are:

1. ACR50 response rate;
2. ACR70 response rate;
3. Proportion of subjects achieving ACR20 response rate of Week 1.

For binary endpoints, frequencies and percentages will be reported for each randomized treatment group. Similar analyses as for the primary endpoint will be conducted.

For the major RA continuous endpoints DAS28 and HAQ-DI change from baseline, statistical inference will be conducted using analysis of covariance (ANCOVA) coupled with MI for missing data handling. Specifically, the ANCOVA model will include treatment as the fixed factor, and the corresponding baseline value and the stratification factor prior bDMARD use (Yes/No) as the covariates. For other continuous endpoints, statistical inference will be conducted using the MMRM model as described in

Section 9.1.2, with the main stratification factor being prior bDMARD use (Yes/No). From both the MI and MMRM analyses, the LS mean and 95% CI will be reported for each randomized treatment group; the LS mean treatment difference and associated 95% CI and p-value will be reported comparing each upadacitinib dose group with the combined placebo group. Both nominal p-value and adjusted p-value through the graphical multiplicity procedure described in Section 9.2.5 will be provided.

